3.2.2.2. Individual Stopping Criteria

- Any subject who experiences any of the criteria listed in [Section 3.2.2.1](#).
- Investigator discretion based on clinical safety grounds.

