1.5. Risk/Benefit Assessment

Further information about the known and expected benefits and risks and reasonably expected AEs of ivermectin may be found in the current IB and the Summary of Product Characteristics.¹⁹

Details of these risks and the proposed strategy to mitigate/monitor these risks are detailed in [Table 1](#).

In this study, safety will be monitored closely both by subjective reporting and by objective means i.e., serial assessments of vital signs, clinical laboratory evaluations data, physical examinations, 12-lead electrocardiogram (ECG) and comprehensive neurological examinations. This study will be run in a Clinical Research Unit (CRU) with immediate access to hospital facilities for the treatment of medical emergencies. Subjects will remain monitored in the clinic for the first 7 days of dosing and will only be discharged from the CRU at the end of Day 7 if the Investigator deems it safe to do so.

Table 1: Risk/Benefit Assessment

Potential Risk of Clinical Significance	Summary of Data/Rationale for Risk	Mitigation Strategy
Skin rashes and pruritus	SmPC	Physical examinations will be performed regularly throughout the study to identify any rashes and overall TEAEs will be monitored.
Cardiovascular changes	SmPC	Heart rate and blood pressure will be frequently monitored during the study by supine and standing vital signs.
CNS changes	SmPC	Comprehensive neurological examinations will occur frequently during the study to identify any changes.
Gastrointestinal system effects	SmPC	Clinical monitoring of body weight and standard safety laboratory parameters, as well as overall TEAEs will be monitored. Subjects will be withdrawn if effects are severe.
Respiratory system changes; exacerbation of asthma	SmPC	Asthmatic subjects will be excluded.
Ophthalmologic changes	SmPC; IB	Comprehensive neurological examinations will occur frequently during the study to identify any changes.
Haematological changes	SmPC	Subjects will be closely monitored with frequent blood tests during the study. Haematology parameters will be closely monitored throughout the course of the study as dose escalation proceeds. Escalation to higher doses and exposures will only occur if emerging data indicates this is safe and appropriate. Stopping criteria have been added for clinically significant lab results. If indicated, no further dose escalation will occur.

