3.2.2. Dose Escalation and Adjustment Criteria

3.2.2.1. Criteria for Stopping Dose Escalation

- PK Stopping Criteria: based on review of the accumulation ratio (RA). Dose escalation will not proceed if this is deemed to pose a clinically significant risk to subjects by the SRC members.
- Safety Stopping Criteria: Dose escalation will not proceed if any of the following occur in ivermectin-treated subjects:
 - One or more Hy's Law cases in subjects who have been administered ivermectin. Hy's Law is defined as AST or ALT ≥ 3 x upper limit of normal (ULN) and bilirubin ≥ 2 x ULN, in the absence of a significant increase in alkaline phosphatase (ALP) and in the absence of an alternative diagnosis that could explain the increase in bilirubin.
 - A 'serious' adverse reaction (see [Section 7.6.1.2](#) for definition of 'serious') in 1 subject, i.e., a serious adverse event (SAE) that is considered at least possibly related to ivermectin administration.
 - 'Severe' non-serious adverse reaction, i.e., a severe non-serious AE considered as at least possibly related to ivermectin administration, in 2 subjects in the same cohort, independent of within, or not within, the same system-organ class (SOC).
 - Clinically significant abnormalities in laboratory parameters in 2 or more subjects within the same cohort indicating dose-related intolerance, considered related to ivermectin.
 - Other findings that indicate dose escalation should be halted, e.g., if there is an unacceptable tolerability profile based on the nature, frequency and intensity of observed AEs and/or clinical safety monitoring.

If any of these stopping criteria are met, the SRC should stop further dose escalation. The SRC will determine whether the dose level should be repeated, whether a lower dose should be tested, or whether the study should be terminated. Progression to subsequent cohorts (which may include lower doses) may be approved by the SRC subject to satisfactory review of the available PK, safety and tolerability data. Alternatively, the SRC may conclude it is inappropriate to continue to another cohort, in which case the study will be terminated. If significant safety concerns arise during dosing of a cohort, the SRC will review all available data and, considering the criteria above, decide whether it is appropriate to continue.

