 - Note: The terms "serious" and "severe" ARE NOT synonymous. The term "severe" is often used to describe the intensity (severity) of a specific event (as in mild, moderate or severe myocardial infarction); the event itself, however, may be of relatively minor medical significance (such as severe headache). This is NOT the same as "serious", which is based on subject/event outcome or action criteria described above and are usually associated with events that pose a threat to a subject's life or functioning. A severe AE does not necessarily need to be considered serious. For example, persistent nausea of several hours duration may be considered severe nausea but not an SAE. On the other hand, a stroke resulting in only a minor degree of disability may be considered mild but would be defined as an SAE based on the above criteria. Seriousness (not severity) serves as a guide for defining regulatory reporting obligations.

7.6.1.3. Clinical Laboratory Abnormalities and Other Abnormal Assessments as Adverse Events and Serious Adverse Events

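### The individual stopping rule borrows the escalation criteria unchanged, so two of them need a second affected subject and the safety criteria need a treatment assignment that the Investigator cannot see

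*Protocol*

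**What the plan says.** Protocol Section 3.2.2.2 (Individual Stopping Criteria) has two bullets. The first covers "Any subject who experiences any of the criteria listed in" Section 3.2.2.1. The second is Investigator discretion on safety grounds.

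Section 3.2.2.1 sets out when dose escalation stops. Its safety criteria are introduced as applying to ivermectin-treated subjects. The severe non-serious related reaction counts when it occurs "in 2 subjects in the same cohort, independent of within, or not within, the same system-organ class". The laboratory criterion reads "Clinically significant abnormalities in laboratory parameters in 2 or more subjects within the same cohort indicating dose-related intolerance", with the further condition that the abnormalities are considered related to ivermectin. There is also an uncounted criterion, "Other findings that indicate dose escalation should be halted", and a provision for review while a cohort is being dosed: "If significant safety concerns arise during dosing of a cohort, the SRC will review all available data".

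Other provisions that bear on stopping one subject:

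- Section 1.5, Table 1, gastrointestinal row: "Subjects will be withdrawn if effects are severe".
- Section 1.5, Table 1, haematology and liver rows: stopping criteria for clinically significant laboratory results are cited as a mitigation.
- Section 6.4: an adverse event may lead to withdrawal on the Investigator's medical judgement. The only numeric rule there concerns missed doses.
- Section 7.6.1.3 and Appendix 4: a decision tree for stopping study medication after liver abnormalities. The flowchart is not shown in the public text.
- Section 5.5: the Investigator and subjects are blinded. Only pharmacy staff and the staff analysing PK samples are unblinded.

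**The concern.** A count of two subjects is a property of a cohort. It suits a decision about the next dose level, but one person cannot satisfy it. Carried over unchanged into a rule about individuals, it leaves two of the listed criteria with no clear effect for a lone affected subject.

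The restriction to ivermectin-treated subjects adds a second difficulty. The person applying the rule is blinded and cannot tell whether the subject in front of them qualifies.

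Section 3.1 says that safety over 28 consecutive days of dosing has not yet been studied in humans, and most doses are taken at home. The events affected include neurological reactions, for which Table 1 offers only examinations as mitigation, and non-liver laboratory findings, for which Table 1 points to stopping criteria.

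**Working it through.** The plan gives no operating characteristic for these rules, so there is no figure to reproduce. The check is a reading of each criterion at the level of one subject.

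| Criterion in 3.2.2.1 | Can one subject meet it as written? |
|---|---|
| Accumulation ratio (PK) | Committee judgement, no count |
| Hy's Law case | Yes, one is enough |
| Serious related reaction | Yes, one is enough |
| Severe non-serious related reaction | No, needs 2 in the cohort |
| Clinically significant related laboratory abnormality | No, needs 2 or more in the cohort |
| Other findings | Judgement, no count |

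Total: 1 PK + 5 safety = 6. Two can be met by one subject, two carry a count of 2, and two are uncounted judgements. The limit to ivermectin-treated subjects applies to all five safety criteria, including the two that one subject can meet.

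**Sentinel stage.** Section 3 doses 1 ivermectin and 1 placebo subject first, and the other six start only after review of data to at least 4 hours after the Day 7 dose. Until then the largest possible ivermectin count is 1, and 1 < 2.

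**Other provisions.** Table 1 withdraws subjects for severe effects in the gastrointestinal row only. Appendix 4 covers the liver. Section 6.4 and the second bullet of 3.2.2.2 are discretionary. Outside the liver provisions, the only laboratory stopping criterion in the visible text is the two-subject count. Table 1's haematology mitigation therefore has no explicit single-subject rule behind it.

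**Home dosing.** Days 8 to 27 are 20 days; less Days 14 and 21 in the unit, 18 of the 28 doses are self-administered.

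**Scale, for illustration.** The documents give no reaction rate. Assume an independent rate p per ivermectin subject of 2%, 5% or 10%.

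- Chance that an affected ivermectin subject has no second case among the other 5, (1 − p)^5: 0.98^5 = 0.904; 0.95^5 = 0.774; 0.90^5 = 0.590.
- Chance of two or more affected among 6, 1 − (1 − p)^6 − 6p(1 − p)^5: 0.0057; 0.0328; 0.1143.

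The first line shows how often the count would stay unmet for a subject who has the event. It does not show that the subject would stay on drug. The second line is used below for the cost of the fix.

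**The case against.** The strongest reply is that the literal reading defeats the clause. The section is about individuals, and a subject experiences a reaction, not a count. If the number is dropped, every criterion has work to do. Table 1 gives some support: it mentions laboratory stopping criteria and then, separately, a halt to escalation, as if the two differed. This reading is plausible and probably what was meant. But the text does not say it, Table 1 supplies no per-subject threshold, and a stopping rule should not need its user to disregard a stated number.

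The second reply is that a lone subject can always be stopped. That stands. Discretion in 3.2.2.2, Section 6.4, the uncounted criterion and mid-cohort committee review are all available. The sentinels are resident to Day 7, and subjects at home are contacted regularly and seen on Days 14 and 21. What is missing is the explicit rule that the first bullet appears to provide; discretion is already a separate bullet.

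Third, severity, relatedness and clinical significance are all judged by the Investigator, so an explicit rule would still rest partly on judgement. That is true, but such a rule fixes the action once the judgement has been made.

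A reader might also infer that the protocol contradicts itself over severe nausea. Section 7.6.1.2 says that "persistent nausea of several hours duration may be considered severe nausea but not an SAE", and Table 1 would withdraw that subject while 3.2.2.2 as written would not. The documents do not support a contradiction. Table 1 adds a ground for withdrawal that 3.2.2.2 does not forbid, the nausea text only separates severe from serious and says nothing about relatedness, and severe gastrointestinal effects lie outside the gap described here.

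**Conclusion.** The point holds as a defect in the written rule, and it should be corrected. Two of the six criteria cannot be met by one subject as written, and the five safety criteria depend on a treatment assignment that the Investigator does not have. For a single severe non-serious related reaction, or a single related clinically significant laboratory abnormality, outside severe gastrointestinal effects and the liver provisions, the visible text leaves stopping to judgement.

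It would go too far to infer that such a subject would be kept on ivermectin, or that individual safety is unsupervised. Discretion applies at every stage, and the 90%, 77% and 59% figures rest on assumed rates and describe the count, not anyone's continued dosing.

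The conclusion is drawn from the visible text. The Appendix 4 thresholds are not shown and are not judged, and redacted sections could contain further rules.

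**What to change.** Replace the cross-reference in Section 3.2.2.2 with a rule that a subject stops study drug, whatever the number of other subjects affected and without unblinding, for any of:

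1. a Hy's Law case or the liver criteria of Appendix 4;
2. a serious adverse event at least possibly related to study drug;
3. a severe non-serious adverse event at least possibly related to study drug;
4. a clinically significant laboratory abnormality considered related to study drug;
5. Investigator discretion.

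Keep the two-subject counts in Section 3.2.2.1 for escalation only, and keep the mid-cohort committee review.

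The change is to protocol wording. Its downside is that Section 7.6.2 defines both severe and possibly related broadly. Section 7.6.1.2 itself notes that a severe event "may be of relatively minor medical significance (such as severe headache"), so a subject may occasionally be stopped for something minor. Section 6.4 requires 5 ivermectin and 1 placebo subjects to complete a cohort. One ivermectin stop leaves 6 − 1 = 5 and one placebo stop leaves 2 − 1 = 1, and both meet the minimum. A second ivermectin stop leaves 4 and would call for a replacement. At the assumed rates of 2%, 5% and 10%, that happens in 0.6%, 3.3% and 11.4% of cohorts. Those figures count one event type only; withdrawals for compliance, consent or other reasons draw on the same minimum and would raise them.

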4. STUDY SETTING

A single clinical research facility will be selected for this study.

5. STUDY TREATMENTS

5.1. Name and Description of Investigational Products

Ivermectin will be provided as 3 mg tablets [REDACTED]

Matching placebo will be manufactured by [REDACTED] and supplied with a certificate of analysis.

Further supportive information will be provided in the Pharmacy Manual.

The IMP supplied by the Sponsor is to be used exclusively in the clinical study according to the instructions in this Protocol and the Pharmacy Manual. Until the IMP is dispensed to the subjects, it should be stored at a controlled room temperature below 25°C. At home, subjects IMP will be stored at room temperature and kept out of the reach and sight of children.

The Principal Investigator will be responsible for storage and accountability of the IMP. Safety information regarding the IMP is provided in the IB.

5.2. Dose Administration

The active IMP or matched placebo will be orally administered in the morning from Day 1 to Day 28 following an overnight fast. Each dose will be taken with 240 mL of water at room temperature. Water will be allowed ad libitum and breakfast can be eaten between 1 to 2 hours after dosing. Dosing will be observed by CRU staff whilst resident in the CRU.

Body weight at Screening will be used to calculate the dose administered. For each dose level administered, the number of 3 mg tablets shown in [Table 4](#) will be administered.

Table 4: Number of Ivermectin Tablets Per Cohort by Body Weight

	Loading Dose (Day 1)	50 µg/kg Daily Dose (Cohort 1; Day 2 to Day 28)	75 µg/kg Daily Dose (Cohort 2; Day 2 to Day 28)	100 µg/kg Daily Dose (Cohort 3; Day 2 to Day 28)
50 to ≤65 kg	4 tablets	1 tablet	1.5 tablets (first day 1 tablet, the next day 2 tablets, etc.)	2 tablets
≥66 to ≤79 kg	5 tablets	1 tablet	1.5 tablets (first day 1 tablet, the next day 2 tablets, etc.)	2.5 tablets (first day 2 tablets, the next day 3 tablets, etc.)
≥80 to ≤95 kg	6 tablets	2 tablets	2.5 tablets (first day 2 tablets, the next day 3 tablets, etc.)	3 tablets
≥96 to ≤110 kg	7 tablets	2 tablets	2.5 tablets (first day 2 tablets, the next day 3 tablets, etc.)	3.5 tablets (first day 3 tablets, the next day 4 tablets, etc.)

Non-whole weight values will be rounded to the nearest whole number. For example, 95.1 to 95.4 kg would be rounded down to 95 kg and 95.5 to 95.9 kg would be rounded up to 96 kg.

Before leaving the CRU on Day 7, subjects will be provided with a paper diary to record their daily dose of ivermectin or placebo (number of tablets taken, what time they took their dose and what time they had breakfast). Whilst outside the CRU, subjects will be contacted regularly by phone or text message to ensure that they are taking the correct number of tablets and to ensure that they are taking their dose following an overnight fast.

If a subject forgets to take their daily dose of ivermectin or placebo in the morning and has already eaten, they should not take their dose for that day.

The number of tablets to be taken can vary day-to-day. If a subject misses their daily dose of ivermectin or placebo then, on the following day, they should take the number of tablets they missed the day previously (e.g., if they are alternating between 1 tablet and 2 tablets per day and they missed 2 tablets, they should take 2 tablets the following day and 1 tablet the day after).

For the Day 14, Day 21 and Day 28 doses, subjects will NOT take their daily dose of ivermectin or placebo. Instead they will bring their remaining tablets to the clinic and will take their daily dose (overnight fasted) after any applicable pre-dose assessments have been performed by CRU staff. Dosing will be observed by CRU staff on all study visit days.

5.3. Concomitant Medication

The Investigator and study team may review medication use on a case-by-case basis to determine if its use would compromise subject safety or interfere with study procedures or data interpretation (exclusion criteria relating to concomitant medication are presented in [Section 6.2](#)). By exception, the subject may take paracetamol (less or equal 2 g/day) for up to 48 hours prior to first dosing. All concomitant medications used (including over-the-counter [OTC] medications and herbal supplements) will be recorded in the source documents and on the appropriate electronic case report form (eCRF).

5.4. Assessment of Compliance with Treatment

All doses will be administered by study staff under direct observation whilst resident in the CRU. The administration of the study drug will be recorded within the appropriate pages of the eCRF. Subjects will be asked to return all unused medication including empty and partially used containers. For the time when subjects administer at home (Day 8 to Day 27), study medication dispensed at the previous visit will be retrieved by the Investigator and compliance assessed by regular contact with the subject whilst outside the CRU, returned medication count and subject diary completion.

Any deviations from the planned dosing procedure will be recorded within the eCRF.

5.5. Blinding

This study will be double-blinded (Investigator- and subject-blinded). The randomisation list will be kept in a secure location until the end of the study. Only the Pharmacy staff involved in handling the study drug and laboratory staff responsible for analysing the PK blood samples will be unblinded during the study and will have access to the randomisation list.

5.6. Emergency Unblinding

The study blind should not be broken except in a medical emergency where knowledge of the IMP would inform treatment of an emergency. The Investigator has the sole responsibility for determining if unblinding of treatment is necessary for medical management of an event. The Investigator will inform the Medical Monitor and Sponsor of this decision as soon as is reasonably practicable. The applicable Standard Operating Procedures (SOPs) will be followed to break the blind.

After database lock, the overall randomisation code will be broken only for reporting purposes.

6. SELECTION AND WITHDRAWAL OF SUBJECTS

The study population includes 24 healthy male subjects. Each subject should meet all the inclusion criteria and none of the exclusion criteria for this study. Under no circumstances can there be exceptions to this rule.

6.1. Inclusion Criteria

Subjects meeting the following criteria will be included in the study:

1. Subject is male, of any ethnic origin.
2. Subject is aged between 18 to 45 years, inclusive.
3. Subject has a body mass index (BMI) of 18.5 to 32.0 kg/m², inclusive.
4. Subject is ≥ 50 kg.
5. Negative RT-PCR Test for SARS-CoV-2 at Screening and negative lateral flow immunoassay test for SARS-CoV-2 at Day -1.
6. Willing and able to comply with scheduled visits, treatment plan, and other study procedures
7. Healthy as determined by a responsible physician, based on medical evaluation including medical history, physical examinations, neurological examinations, concomitant medication, vital signs, 12-lead ECG and clinical laboratory evaluations.
8. Male subjects must use a condom during the study and for 3 months after their final dose of study medication, if their partner is a woman of childbearing potential. In addition, their female partner of childbearing potential must use an additional method of highly effective contraception (see [Section 6.3.1](#)) from first dosing until 3 months following final dosing.
9. Provision of giving written informed consent, which includes compliance with the requirements and restrictions listed in the consent form.

6.2. Exclusion Criteria

Subjects with any of the following will be excluded from study participation:

1. Clinically relevant history of abnormal physical or mental health (defined as any subject requiring medical, psychological or pharmacotherapeutic intervention for mental illness) interfering with the study as determined by medical history and physical examinations obtained during Screening and Day -1 as judged by the Investigator (including [but not limited to], neurological, psychiatric, endocrine, cardiovascular, respiratory, gastrointestinal, hepatic, or renal disorder).
2. Clinically relevant abnormal laboratory results (including hepatic and renal panels, complete blood count, chemistry panel and urinalysis), 12-lead ECG and vital signs, or physical findings at Screening and/or Day -1 (as judged by the Investigator). In case of uncertain or questionable results, tests performed during Screening may be repeated once to confirm eligibility or judged to be clinically irrelevant for healthy subjects.

3. Refractory nausea, vomiting, or chronic gastrointestinal disorders, inability to swallow the study drug or having undergone extensive bowel resection which may affect adequate absorption of ivermectin
4. Any other concomitant disease or condition that could interfere with, or for which the treatment might interfere with, the conduct of the study as outlined in this Protocol, or that would, in the opinion of the Investigator, pose an unacceptable risk to the subject in this study.
5. Subjects with Gilbert's syndrome or AST, ALT, gamma-glutamyl transferase (GGT) or total bilirubin levels greater than the ULN at Screening or Day -1. These laboratory evaluations may be repeated once at the discretion of the Investigator. If the repeat test is within the reference range, the subject may be included only if the Investigator considers that the previous finding will not introduce additional risk factors and will not interfere with interpretation of safety data.
6. Known hypersensitivity or allergy to any component of the ivermectin drug product or placebo.
7. Evidence of previous SARS-CoV-2 infection from medical history.
8. Ophthalmologic disorder (moderate and severe retina or optic nerve pathology; cataracts excluded).
9. Subjects with a diagnosis of asthma or any other respiratory condition.
10. A neurologic disorder that may compromise blood brain barrier permeability (stroke within 90 days, brain tumour, multiple sclerosis, or other neuroinflammatory condition, a neurodegenerative disorder, epilepsy) or history of seizures.
11. QTcF >450 msec at Screening or at check-in on Day -1, following triplicate ECG readings.
12. Positive test for hepatitis B surface antigen (HBsAg), anti-hepatitis C antibody (anti-HCV) or human immunodeficiency virus I and II (anti-HIV I/II) at Screening.
13. Positive urine test for drugs of abuse, urine cotinine test or alcohol breath test at Screening or Day -1.
14. History of drug and/or alcohol abuse within the last 2 years, or intake of >21 units of alcohol weekly, and the inability to refrain from alcohol use from 48 hours before Screening and from 48 hours before Day -1 until the end of the study. One unit is equivalent to a 285 mL glass of full-strength beer or 1 (30 mL) measure of spirits or 1 glass (100 mL) of wine.
15. Use of tobacco and/or nicotine containing products (including e-cigarettes) within 3 months of Screening.
16. Habitual and heavy consumption of caffeinated beverages (>8 cups of coffee or equivalent per day) at Screening; and/or unable to refrain from use of (methyl) xanthine (e.g., coffee, tea, cola, chocolate) from 48 hours prior to each clinic visit until the end of the study.

17. The subject has participated in a clinical study and has received a medication or a new chemical entity within 3 months or 5 half-lives (whichever is longer) prior to first dosing of current study medication.
18. Use of any prescription or non-prescription medications, including herbal and nutritional supplements, or OTC medications (e.g., ibuprofen, aspirin) within 14 days of first dosing and throughout the study. By exception, the subject may take paracetamol (less or equal 2 g/day) for up to 48 hours prior to first dosing. The Investigator and study team may review medication on a case-by-case basis to determine if its use would compromise subject safety or interfere with study procedures or data interpretation.
19. Use of any drugs that are known substrates of CYP3A4, P-glycoprotein (P-gp) from within 4 weeks of Screening and unable to refrain from them until the end of the study (e.g., rifampicin, quinidine, amiodarone, diltiazem, spironolactone, verapamil, clarithromycin, erythromycin, itraconazole, ketoconazole, cyclosporine, tacrolimus, indinavir, ritonavir or cobicistat). Use of critical CYP3A4 substrate drugs such as warfarin or coumarin anticoagulants.
20. Recent or expected microfilaricidal drug use, including ivermectin, or travel history to areas that are endemic for Loa loa or onchocerciasis (Angola, Cameroon, Central African Republic, Chad, Democratic Republic of Congo, Ethiopia, Equatorial, Guinea, Gabon, Republic of Congo, Nigeria and Sudan).
21. Use of medications having potential activity against SARS-CoV-2 such as hydroxychloroquine, chloroquine, lopinavir, ritonavir, remdesivir, azithromycin, in the 30 days prior to Screening and unable to refrain from them until the end of the study.
22. History of severe adverse reactions or allergies, or history of an anaphylactic reaction to prescription or non-prescription medication or food (non-active hay-fever is acceptable).
23. Consumption of any food or drinks containing cranberry, pomegranate, starfruit, grapefruit, pomelos, exotic citrus fruits or Seville oranges (including marmalade and juices made from these fruits) within 14 days prior to first dosing until the end of the study.
24. Strenuous exercise within 48 hours prior to each blood collection for clinical laboratory tests.
25. Donation of blood or plasma of >400 mL within 4 weeks prior to first dosing until 4 weeks after final dosing.
26. Male subject who will not abstain from sperm donation between first dosing and 3 months after final dosing.

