1.3.2. Pharmacokinetics in Animals

Oral bioavailability of ivermectin is low in rats and dogs (25% to 41%). Ivermectin is widely distributed to tissues and no blood brain barrier passage is noted after either oral or intravenous administration in rats.^{12,13} After administration to pregnant rats, transfer of ivermectin through the placenta is low and ivermectin was found to be quantitatively transferred to milk.

Ivermectin is highly bound to plasma proteins (99.9%) in mouse, rat, rabbit, dog, minipig and human, with low in vitro partitioning into red blood cells. The fraction of ivermectin that is metabolised is higher after oral administration indicating a hepatic first-pass effect. Demethylation and hydroxylation appear to be the main metabolic reactions and no significant gender differences in metabolism are noted in rats. Cytochrome P450 (CYP)3A4 was identified as the enzyme primarily responsible for the metabolism of ivermectin. CYP2D6 and CYP2E1 were also shown to be involved in the metabolism of ivermectin but to a significantly lower extent compared to CYP3A4. Ivermectin is slowly eliminated, the primary route of excretion being in the faeces. The majority of radioactivity associated with ivermectin is excreted within 48 hours after oral administration to rats.

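### In exclusion criteria 19 (first sentence) and 21, recent use excludes only together with inability to stop, so the 4-week and 30-day look-backs add almost nothing to criterion 18's 14-day rule

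*Protocol*

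**What the plan says.** All the criteria below are in Protocol 6.2.

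- **Criterion 19, first sentence**, covers CYP3A4 and P-gp drugs and gives a list of named examples. It applies to use "from within 4 weeks of Screening and unable to refrain from them until the end of the study".
- **Criterion 19, second sentence**, has no such condition: "Use of critical CYP3A4 substrate drugs such as warfarin or coumarin anticoagulants".
- **Criterion 21**, on drugs with potential activity against SARS-CoV-2, applies to use "in the 30 days prior to Screening and unable to refrain from them until the end of the study".
- **Criterion 16**, on caffeine, joins its two parts differently: "at Screening; and/or unable to refrain from use of (methyl) xanthine".
- **Criterion 18** bars any prescription, over-the-counter, herbal or supplement use "within 14 days of first dosing and throughout the study". It has a paracetamol exception and a review clause: "The Investigator and study team may review medication on a case-by-case basis to determine if its use would compromise subject safety".

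Protocol 6 allows no exceptions to the eligibility criteria. Protocol 3 places Screening within 28 days before first dosing.

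On the drug class, criterion 19 opens with "Use of any drugs that are known substrates of CYP3A4, P-glycoprotein (P-gp", and the drug-interaction row of Table 1 (Protocol 1.5) also speaks only of substrates. Protocol 1.3.2 states: "Cytochrome P450 (CYP)3A4 was identified as the enzyme primarily responsible for the metabolism of ivermectin".

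**The concern.** A look-back of 4 weeks or 30 days before Screening is presumably there to impose a longer drug-free period than the general 14 days. Joined by *and* to inability to refrain, it does not. A volunteer who recently took a listed drug and agrees to stop meets only one of the two conditions, so neither criterion excludes him.

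The stake is mainly the primary objective. The PK profile at each dose level rests on 6 active subjects, so one man entering with a residual effect on ivermectin's metabolism or transport could move that level's Cmax, AUC0-24h and half-life summaries.

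There is a secondary mismatch. If CYP3A4 metabolises ivermectin, ivermectin's exposure depends on what changes CYP3A4 activity. A class label that names only fellow substrates does not describe that interaction.

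**Working it through.** The plan gives no figure to reproduce here. Protocol 11.2 says the sample size was not determined statistically; the only related arithmetic, 3 × (6 + 2) = 24, agrees with planned enrolment.

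**Step 1. Whom do the look-backs exclude?** This table applies to the first sentence of criterion 19 and to criterion 21.

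| Volunteer | 19/21 as written | Criterion 18 | 19/21 with *and/or* |
|---|---|---|---|
| Recent use, able to stop | not excluded | excluded only if last use is within 14 days of first dose | excluded |
| Recent use, unable to stop | excluded | excluded, because use continues in the study | excluded |
| No recent use, unable to refrain | not excluded | excluded once he uses it | excluded |

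As written, criteria 19 and 21 exclude only the second row, which criterion 18 already covers. They add something only where case-by-case review would have let a man through.

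**Step 2. Width of the gap.** With Screening about 1 to 28 days before Day 1, the look-back limits are:

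- criterion 19: 28 + 1 = 29 to 28 + 28 = 56 days before Day 1
- criterion 21: 30 + 1 = 31 to 30 + 28 = 58 days before Day 1

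The literal text guarantees only the 14 days of criterion 18. The gap is last use between 14 days before Day 1 and these limits.

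**Step 3. Drug left on Day 1.** Fraction left = 0.5^(days / half-life). The documents give no half-lives for the listed drugs, so these are assumed.

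| Assumed half-life (days) | after 14 days | after 29 days | after 56 days |
|---|---|---|---|
| 1 | 0.01% | about 0% | about 0% |
| 2.8 | 3.1% | 0.08% | about 0% |
| 7 | 25% | 5.7% | 0.4% |
| 14 | 50% | 24% | 6% |
| 30 | 72% | 51% | 27% |

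Five half-lives fit within 14 days only if the half-life is at most 14/5 = 2.8 days. With the full criterion 19 window that limit becomes 29/5 = 5.8 to 56/5 = 11.2 days; for criterion 21 it becomes 31/5 = 6.2 to 58/5 = 11.6 days. The repaired window would still not clear the longest half-lives.

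**Step 4. Effect on a dose level.** If one of n active subjects has exposure multiplied by an assumed factor f, the geometric mean is multiplied by f^(1/n).

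| f | n = 6 (full cohort) | n = 4 (minimum for escalation, Protocol 3 and 6.4) |
|---|---|---|
| 0.5 | 0.891 (−11%) | 0.841 (−16%) |
| 2 | 1.122 (+12%) | 1.189 (+19%) |
| 3 | 1.201 (+20%) | 1.316 (+32%) |

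The documents do not connect the drug left in Step 3 to f in Step 4, so the two steps show scale and do not predict a bias.

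**Step 5. Class label.** Protocol 1.3.2 makes ivermectin the CYP3A4 substrate. For P-gp the documents offer only indirect support: the 10 to 100-fold greater sensitivity of P-gp-deficient mice in Table 1. Criterion 19 and Table 1 name substrates, and neither names drugs that change CYP3A4 or P-gp activity. The named examples in criterion 19 are covered whatever the label.

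**The case against.** A reader might infer that the wording lets interacting drugs carry over freely into the PK and infection results. The documents do not support that.

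- **Criterion 18 bounds the gap.** It removes every class of medication in the 14 days before dosing, with no inability-to-stop condition. This stands; the remaining exposure is the interval in Step 2, plus anything case-by-case review allows.
- **Other provisions help.** Inclusion criterion 7 weighs medical history and concomitant medication, exclusion criteria 1 and 4 reach interfering conditions, and Protocol 5.3 lets the team review medication for its effect on data interpretation. This is partial protection that relies on judgement and does not restore a fixed look-back.
- **The protocol may use *and* loosely.** Criterion 14 joins alcohol history to inability to refrain in the same way, and its literal reading is implausible. Sites may therefore apply 19 and 21 as intended. That is fair, but with no exceptions allowed and *and/or* used in criterion 16, the text should not depend on it.
- **The shift is within sampling error.** Protocol 1.4 gives a Cmax of 46.6 ± 21.9 ng/mL after a single 12 mg dose. Taking ± as an SD, CV = 21.9/46.6 = 0.47, log-scale SD = √ln(1 + 0.47²) = 0.45, and the standard error for n = 6 is 0.45/√6 = 0.18, roughly 20%. The assumed 12% is smaller. This stands as a limit on severity. Medications are also recorded and listed, so such a subject could be identified.
- **The substrate label creates no carry-over.** Criterion 18 applies to every class and the examples are named individually. This stands; the label supports only a request to reconcile wording.
- **The infection endpoint is exploratory**, summarised descriptively in 18 active and 6 placebo subjects. It gives no useful support to the point.

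**Conclusion.** The point holds in a limited form. In the first sentence of criterion 19 and in criterion 21, the look-backs have almost no effect as written, because those they exclude are already excluded by criterion 18. A volunteer who last used a listed drug between 14 days before Day 1 and about 29–56 days (criterion 19) or 31–58 days (criterion 21) before it can enter if he agrees to stop.

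The consequence is negligible for short half-life drugs and possible for long half-life ones. It bears mainly on primary PK with 6 active subjects per level. The half-lives and the two-fold change in one subject are assumptions, and residual drug is only a stand-in for residual effect.

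Three stronger conclusions are not supported: that carry-over is generally admitted, that all of criterion 19 is conditional (its second sentence is not), and that the infection count is materially at risk. The substrate wording is a secondary inconsistency with Protocol 1.3.2.

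**What to change.** 1. In the first sentence of criterion 19 and in criterion 21, replace *and* before the inability-to-refrain clause with *and/or*, as in criterion 16, so that either condition excludes.
2. Check criterion 14 for the same construction, and state how the case-by-case clause of criterion 18 relates to criteria 19 and 21.
3. Reconcile criterion 19, its example list and the drug-interaction row of Table 1 with Protocol 1.3.2 on which drug class is meant. The clinical team should settle the class.

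The cost is protocol wording in two or three criteria and one table row, and possibly a few more screen failures among volunteers with recent medication. No analysis changes.
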